#### **9.7.2.3. Secondary Analysis**

The main analysis will compare the occurrence of safety outcomes in the COMIRNATY 2023-2024 Formula-exposed group to that of the matched comparator group. Secondary analyses will conduct this comparison separately, including recalculation of the matching ratio and accounting for individuals who are included in both study cohorts for various subsets of the matched comparator group, including:

- Comparators who, on cohort entry, received a 2023-2024 formulation of a COVID-19 vaccine other than COMIRNATY (i.e., Moderna or Novavax)
- Comparators who received a non-COVID-19 vaccine on cohort entry
- Comparators who did not receive a vaccine on cohort entry but had another type of outpatient health encounter.

090177e1a5be86fe\Approved\Approved On: 19-Mar-2026 15:57 (GMT)

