#### **9.2.2.2. Exclusion Criteria**

Patients meeting any of the following criteria will not be included in Phase 2 of the study:

1. Are of unknown sex.
2. Have a missing month and year of birth.
3. Have received a COVID-19 vaccine in the 270 days prior to cohort entry date (as defined in Section 9.2.3).
4. Have received both the COMIRNATY 2023-2024 Formula and a COVID-19 vaccine other than the COMIRNATY 2023-2024 Formula on the cohort entry date (defined in Section 9.2.3).

In both phases of the study, when creating the analytic population for each specific safety outcome of interest, individuals will be excluded if they experienced that safety outcome during the portion of the baseline period designated as the clean period ([Section 9.2.4](#)).

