### 9.3.1.2. Comparator Cohort

The Phase 2 cohort study will include comparators with no recorded vaccination for the COMIRNATY 2023-2024 Formula. To improve comparability with the COMIRNATY 2023-2024 Formula vaccinated cohort, patients included in the comparator cohort will be required to have a code indicative of a healthcare encounter, including one of the following:

- Presence of a code for a vaccine other than the COMIRNATY 2023-2024 Formula;
- Presence of a code indicative of an outpatient healthcare encounter.

Codes relating to other vaccines or outpatient visits are provided in [Annex 2 \(Appendix II\)](#).

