#### 9.7.2.4. Subgroup Analysis

If sample size permits, the main analysis will be restricted to the following subgroups:

- Individuals with concomitant administration of a non-COVID-19 vaccine (e.g., seasonal influenza, RSV) on cohort entry date; specific analyses will be performed among individuals receiving seasonal influenza vaccine and those receiving RSV vaccine
- Immunocompromised individuals
- Individuals with specific baseline comorbidities, such as a chronic lung, heart, kidney or liver condition; cancer; Down syndrome or other neurological or neurodevelopmental disorders; and blood disorders
- Individuals with prior SARS-CoV-2 infection
- Individuals with prior COVID-19 vaccination
- Pregnant women
- Individuals aged < 18 years
- Individuals aged  $\geq$  65 years

For the subgroup analysis, the propensity score will be included in the model as a covariate, given that some matched strata may be broken by restricting both the COMIRNATY 2023-2024 Formula cohort and the comparator cohort by the above attributes. As with the primary analysis, unconditional Poisson regression will be used, and the model will account for individuals who are included in both groups.

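### Section 9.7.2.3: the non-COVID-19-vaccine comparator subset does not exclude people given Moderna or Novavax the same day, so subsets 1 and 2 can overlap and subset 2 can be diluted toward 1

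*Protocol*

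**What the plan says.** The secondary analyses in Section 9.7.2.3 repeat the Phase 2 comparison separately "for various subsets of the matched comparator group, including" three groups:

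1. "Comparators who, on cohort entry, received a 2023-2024 formulation of a COVID-19 vaccine other than COMIRNATY (i.e., Moderna or Novavax");
2. "Comparators who received a non-COVID-19 vaccine on cohort entry";
3. "Comparators who did not receive a vaccine on cohort entry but had another type of outpatient health encounter".

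The groups are not said to be mutually exclusive, and no order of precedence is given. The abstract describes the second group in the same terms.

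Three other provisions bear on who can be in group 2:

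- Section 9.3.1.2 admits a comparator on "Presence of a code for a vaccine other than the COMIRNATY 2023-2024 Formula", so other COVID-19 vaccines and non-COVID-19 vaccines share one entry rule.
- Section 9.2.2.2, criterion 3, excludes people who "Have received a COVID-19 vaccine in the 270 days prior to cohort entry date".
- Section 9.2.2.2, criterion 4, excludes people who "Have received both the COMIRNATY 2023-2024 Formula and a COVID-19 vaccine other than the COMIRNATY 2023-2024 Formula on the cohort entry date".

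Section 9.7.2.4 also plans a subgroup of "Individuals with concomitant administration of a non-COVID-19 vaccine (e.g., seasonal influenza, RSV) on cohort entry date", so the protocol expects vaccines to be given together.

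**The concern.** The three subsets are informative because they differ: another COVID-19 vaccine, a vaccine against something else, and no vaccine. Only the second could set COMIRNATY recipients against people who sought a vaccine but had no COVID-19 vaccine that day. As defined, it does not ensure this. A comparator given Moderna and influenza vaccine on the entry date satisfies the definitions of both subset 1 and subset 2.

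An adverse effect common to COVID-19 vaccines would then raise the event rate in part of the subset 2 comparator as well as in the COMIRNATY group. The resulting bias is toward 1, which in a safety study is the direction that hides a risk. Two analysts could also classify people with both vaccines differently and report different subset 2 results from the same data.

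**Working it through.** **Step 1. Does any provision remove a comparator given Moderna plus influenza vaccine on the entry date?**

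| Provision | Effect on this person |
|---|---|
| 9.3.1.2, comparator entry | Qualifies through either vaccine code |
| 9.2.2.2, criterion 3 | Not removed: it covers the 270 days before entry, not the entry day |
| 9.2.2.2, criterion 4 | Not removed: it requires COMIRNATY on the same day |
| 9.7.2.3, subset 1 | Included: Moderna at entry |
| 9.7.2.3, subset 2 | Included: non-COVID-19 vaccine at entry |
| 9.7.2.3, subset 3 | Excluded: had a vaccine at entry |

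Only subset 3 carries an explicit negative condition. Followed literally, the plan places this person in subsets 1 and 2. Section 7 describes the document as a combined protocol and SAP, and Annex 1 lists no standalone documents, so this is the working definition.

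**Step 2. How large could the dilution be?** The plan states no figure on this point, so there is none to reproduce. Let q be the share of subset 2 that also had a COVID-19 vaccine at entry, and assume that vaccine carries the same rate ratio R as COMIRNATY. The comparator rate, relative to background, is (1 − q) + qR, so

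expected observed ratio = R / (1 + q(R − 1)).

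The documents do not give q. The values 5%, 15% and 30% are assumptions.

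*(a) Effect constant over the whole of follow-up (an upper illustration):*

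| R | q = 5% | q = 15% | q = 30% |
|---|---|---|---|
| 2 | 2/1.05 = 1.90 | 2/1.15 = 1.74 | 2/1.30 = 1.54 |
| 3 | 3/1.10 = 2.73 | 3/1.30 = 2.31 | 3/1.60 = 1.88 |

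*(b) Effect confined to the risk interval.* Phase 2 follows people for up to one year (Sections 9.1.2 and 9.2.5.2), while the longest risk interval in Table 2 is days 1 to 42. Assume a threefold risk on those 42 days, none afterwards, a constant background rate and a full year of follow-up:

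- averaged ratio = 1 + (3 − 1) × 42/365 = 1.23;
- at q = 15%: 1.23 / (1 + 0.15 × 0.23) = 1.19;
- at q = 30%: 1.23 / (1 + 0.30 × 0.23) = 1.15.

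*(c) No effect.* With R = 1 the expression equals 1 for every q, so there is no bias.

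**Step 3. What happens after the entry day?** Section 9.2.5.2 ends follow-up at a later, different COVID-19 vaccine for COMIRNATY recipients and for comparators who entered on another COVID-19 vaccine. It lists no such rule for comparators who entered on a non-COVID-19 vaccine alone. Some COVID-19-vaccinated time can therefore enter subset 2 later, even with a clean entry-day definition.

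**The case against.** The best defence is that a three-way split is the natural reading: the protocol names three contrasting sets to be analysed separately, and a sensible programmer would keep them apart. That may be the intent, but the text does not say so, and it does not say to which set people with both vaccines belong. The gap stands.

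Several stronger readings are tempting and the documents do not support them:

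- **That subset 2 is contaminated.** The protocol gives no share of people with both vaccines and never states that this subset is meant to be free of COVID-19 vaccine. That purpose is inferred from the label and its place in the list. The supportable statement is that the subset can overlap with subset 1 as worded.
- **That a true ratio of 2 or 3 would be seen as the values in table (a).** Those figures assume a constant effect for up to a year, which fits poorly with risk intervals of 42 days or less. Under (b) the loss is modest.
- **That the concomitant-vaccine subgroup in Section 9.7.2.4 has the same fault.** It restricts the main analysis, whose comparator is anyone without recorded COMIRNATY 2023-2024 Formula and so includes Moderna and Novavax recipients by design. Limiting that one subgroup to subset 2 comparators would change its contrast, and that is a preference, not a correction.
- **That a shared risk would go unseen.** Subset 3 excludes any vaccine at entry, and the SCRI uses no comparator group, so both could still show it.

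**Conclusion.** The omission is real and nothing else in the protocol repairs it: as worded, subsets 1 and 2 can share people, and a risk common to COVID-19 vaccines can dilute the subset 2 rate ratio toward 1. It touches one secondary comparison. A reader might extend it to the primary analysis, but that pools all comparator types by design and is not affected.

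The size cannot be fixed from the documents. On the assumptions in (b) it is modest: about 1.23 becomes 1.19 with 15% overlap and 1.15 with 30%. It would be larger only if the effect persisted well beyond the risk intervals, and it is nil if there is no effect. These figures also assume that the other COVID-19 vaccines carry the same ratio as COMIRNATY.

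**What to change.** In Section 9.7.2.3, and to match in the abstract, define the subsets so that they cannot overlap:

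1. another 2023-2024 COVID-19 vaccine on cohort entry, with or without other vaccines;
2. a non-COVID-19 vaccine and no COVID-19 vaccine on cohort entry;
3. no vaccine on cohort entry (unchanged).

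Apply the definitions before the matching ratio is recalculated for each subset. Annex 2, Appendix II already lists other COVID-19 vaccines separately from other vaccines, so no new data are needed. The cost is one clause and a somewhat smaller subset 2.

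The report should say that this makes subset 2 free of COVID-19 vaccine on the entry day only, because Section 9.2.5.2 does not end follow-up for these comparators at a later COVID-19 vaccine. No change to Section 9.7.2.4 is needed on this account.

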#### 9.7.2.4. Subgroup Analysis

If sample size permits, the main analysis will be restricted to the following subgroups:

- Individuals with concomitant administration of a non-COVID-19 vaccine (e.g., seasonal influenza, RSV) on cohort entry date; specific analyses will be performed among individuals receiving seasonal influenza vaccine and those receiving RSV vaccine
- Immunocompromised individuals
- Individuals with specific baseline comorbidities, such as a chronic lung, heart, kidney or liver condition; cancer; Down syndrome or other neurological or neurodevelopmental disorders; and blood disorders
- Individuals with prior SARS-CoV-2 infection
- Individuals with prior COVID-19 vaccination
- Pregnant women
- Individuals aged < 18 years
- Individuals aged  $\geq$  65 years

For the subgroup analysis, the propensity score will be included in the model as a covariate, given that some matched strata may be broken by restricting both the COMIRNATY 2023-2024 Formula cohort and the comparator cohort by the above attributes. As with the primary analysis, unconditional Poisson regression will be used, and the model will account for individuals who are included in both groups.

Lastly, a descriptive analysis of the matched cohorts will focus specifically on outcomes related to pregnancy (spontaneous abortion, stillbirth, preterm birth, major congenital malformations and small for gestational age). Recipients of the COMIRNATY 2023-2024 Formula and comparators who are pregnant at cohort entry will be identified, and the timing of their vaccination in relation to their last menstrual period (LMP) will be characterized. Baseline characteristics will be descriptively compared among the pregnant COMIRNATY 2023-2024 Formula recipients and comparators. Among COMIRNATY 2023-2024 Formula recipients who are pregnant at cohort entry, as well as among pregnant comparators, the incidence of pregnancy outcomes (spontaneous abortion, stillbirth, preterm birth) during follow-up will be described. For those individuals whose pregnancy results in a live birth, the prevalence of major congenital malformations and small for gestational age in their infants will be descriptively reported. Prevalence estimates will be reported separately for infants whose mothers received the COMIRNATY 2023-2024 Formula when pregnant and infants whose mothers do not have a recorded vaccination of COMIRNATY 2023-2024. Due to the relatively short length of follow-up, comparative analyses relating to pregnancy and infant outcomes will not be performed.

All results from Phase 2 analyses will be presented in the Final Report.

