### 9.1.2. Cohort Design

Phase 2 will consist of a propensity score-matched cohort study of individuals with and without a recorded dose of the COMIRNATY 2023-2024 Formula, conducted within the ORD. During the accrual period of 11 September 2023 through 31 March 2024, individuals who receive the COMIRNATY vaccine will be classified as exposed, and those with no recorded vaccination with the COMIRNATY 2023-2024 Formula but who have a healthcare encounter will be classified as comparators. Propensity score matching will be performed to address control of potential confounding, with matching to be conducted within age group and calendar periods. Age group will be defined as: 6 months–4 years; 5–11 years; 12–17 years; 18–64 years; and  $\geq 65$  years, while calendar periods will be defined by 14-day increments (e.g., 01 September 2023 to 14 September 2023, 15 September 2023 to 28 September 2023). Alternate calendar periods (e.g., one month) may be empirically explored. Thus, within any given calendar period, comparators within the same age group will be matched without replacement to a COMIRNATY recipient on PS, down to a maximum allowable level of precision in the PS ([Section 9.7.2.1](#)). This will ensure a sufficient pool of comparators for stratified and/or subpopulation analyses ([Sections 9.7.2.3 & 9.7.2.4](#)).

These matched cohorts will be followed for up to one year for occurrence of safety outcomes. For this Phase 2 matched cohort study, the safety outcomes of interest are listed in [Section 9.3.2](#).

090177e1a5be86fe\Approved\Approved On: 19-Mar-2026 15:57 (GMT)

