### 9.2.5.2. Cohort Study

In the cohort study (Phase 2), depending on the safety outcome of interest, follow-up will begin on cohort entry or the day following cohort entry ([Table 2](#)) and extend until the earliest of:

- The occurrence of an outcome of interest ([Section 9.3.2](#));
- For COMIRNATY 2023-2024 Formula recipients, receipt of a COVID-19 vaccine other than the COMIRNATY 2023-2024 Formula; for comparators whose qualifying healthcare encounter is for a non-COMIRNATY 2023-2024 Formula COVID-19 vaccination, receipt of a different brand of COVID-19 vaccine from cohort entry;
- One year after cohort entry;
- Disenrollment from the health plan, death, or the end of data collection;

Those comparators who later receive a dose of COMIRNATY 2023-2024 Formula may be eligible for inclusion in the COMIRNATY 2023-2024 Formula cohort if they meet the eligibility criteria for cohort entry.

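### Malformation prevalence is pooled over exposure at any stage of pregnancy, so a first-trimester excess would be pulled toward background

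*Protocol*

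**What the plan says.** Section 9.7.2.4 (Subgroup Analysis) ends with a descriptive pregnancy analysis within the matched cohorts.

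- **Entry.** "Recipients of the COMIRNATY 2023-2024 Formula and comparators who are pregnant at cohort entry will be identified". No gestational limit is set.
- **Timing.** For these women "the timing of their vaccination in relation to their last menstrual period (LMP) will be characterized".
- **Infant outcomes.** The denominator is live births, and the reporting is descriptive: "For those individuals whose pregnancy results in a live birth, the prevalence of major congenital malformations and small for gestational age in their infants".
- **Reporting groups.** There are two. The exposed group is "infants whose mothers received the COMIRNATY 2023-2024 Formula when pregnant". The other group is "infants whose mothers do not have a recorded vaccination of COMIRNATY 2023-2024".
- **Status.** Short follow-up is given as the reason why "comparative analyses relating to pregnancy and infant outcomes will not be performed". Section 9.3.2 makes the pregnancy outcomes conditional on sample size.

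Cohort follow-up in Section 9.2.5.2 stops at the latest at "One year after cohort entry". That section lists stopping rules for cohort members and does not mention infants. Section 7 calls the document a combined protocol and SAP, and Annex 1 lists no standalone documents, so the text does not pass this choice to another document.

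**The concern.** The exposed group for malformations is defined by any dose during pregnancy. A dose late in pregnancy cannot be the cause of most structural malformations, so each later-exposed infant adds mainly background risk to the exposed figure. An excess confined to early exposure is therefore shrunk in proportion to the share of infants exposed early. The protocol plans to derive the variable that would separate the two groups, but does not use it for this outcome.

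Malformations are a named Phase 2 outcome in a study that is a condition of authorization. Two prevalences printed next to each other will be compared, whatever label they carry. A reassuring pooled figure would say less about first-trimester exposure than a reader is likely to assume.

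A second, smaller gap is that no search window is stated for infant diagnoses. If the mother's one-year clock were applied to infants, time available for diagnosis would depend on gestational age at entry.

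**Working it through.** The protocol states no malformation rate, sample size or gestational distribution for this analysis, so there is no figure of its own to reproduce. What follows illustrates size under stated assumptions.

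**Inputs (all assumptions)**
- f: share of exposed live-born infants whose exposure fell in the first trimester.
- RR: true prevalence ratio for first-trimester exposure.
- No excess from later exposure, and comparator infants at background prevalence p0.

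**Step 1. Plausible f.** If vaccination is uniform over gestation, f is window length divided by pregnancy length:
- weeks 2 to 13 of 2 to 40: 11/38 = 28.9%
- weeks 0 to 13 of 0 to 40: 13/40 = 32.5%
- weeks 0 to 14 of 0 to 40: 14/40 = 35.0%

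This gives 29% to 35%. Actual uptake need not be uniform, so 20% to 50% is used as the range. A narrower susceptible window (weeks 4 to 10 of 2 to 40) gives 6/38 = 15.8%.

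**Step 2. Apparent ratio.** Pooled exposed prevalence = f × RR × p0 + (1 − f) × p0. Dividing by p0:

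apparent ratio = 1 + f × (RR − 1)

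| f | RR = 1.5 | RR = 2 | RR = 3 |
|---|---|---|---|
| 0.20 | 1.10 | 1.20 | 1.40 |
| 0.30 | 1.15 | 1.30 | 1.60 |
| 0.35 | 1.175 | 1.35 | 1.70 |
| 0.50 | 1.25 | 1.50 | 2.00 |

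The ratio does not depend on p0. Any f below 1 shrinks it.

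**Step 3. On the prevalence scale.** With p0 = 3% (assumed) and RR = 2, a first-trimester stratum would show 6.0%. The pooled exposed figure would be 3% × 1.20 = 3.6% at f = 0.20 and 3% × 1.50 = 4.5% at f = 0.50.

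**Step 4. Infant observation time, only if the mother's clock applies.** For birth at 40 weeks, days observed after birth = 365 − 7 × (40 − week of entry). Entry at week 4 gives 365 − 252 = 113 days; entry at week 36 gives 365 − 28 = 337 days. The protocol does not say that this clock governs infant outcomes.

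**Step 5. Room for a fixed window.** Accrual ends on 31 March 2024 (Section 9.1.2). Adding 280 days gives 5 January 2025 as an outer due date. From there to 31 August 2025 is 238 days. Section 6, footnote c, defines that August date as when the analytic dataset is first completely available, so the last service date is on or before it and 238 days is a ceiling for that infant. If service dates ended on 31 March 2025 (an assumption), 85 days would remain.

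**The case against.** The strongest answer is that no effect is being estimated. The analysis is descriptive, conditional on sample size, and the protocol expressly declines a comparison. Timing relative to the last menstrual period will be reported, so a reader can see how much of the exposed group was vaccinated early, and splitting a rare outcome thins the cells further. Most of this stands. It limits the weight of the point and makes power calculations irrelevant. It does not remove the point, because knowing the timing mix does not let a reader recover the first-trimester prevalence from a pooled figure.

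Three stronger readings are tempting and are not supported:

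- **That most exposed infants were exposed after the susceptible window.** The protocol gives no gestational distribution. Uniform uptake would put 65% to 71% outside the first trimester, but at a 50% share it is no longer most. Nor is it right that later-exposed infants could not have been affected: malformations arise mainly, not only, from early exposure.
- **That the earliest-exposed infants will be observed for the shortest time.** In Section 9.7.2.4 the reference to follow-up is attached to spontaneous abortion, stillbirth and preterm birth, and the sentence on infant prevalence carries no clock. If the mother's clock did apply, it would apply to comparators' infants as well.
- **That at least 238 days of infant data are assured.** The August 2025 date marks dataset availability, so this is an upper limit for the outermost due date.

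**Conclusion.** The point holds as a reporting weakness worth correcting. As written, the plan gives one malformation prevalence for exposure at any stage of pregnancy and leaves the gestational timing it has derived unused for that outcome. Dilution follows for any first-trimester share below 100%. Its size rests on assumptions: for a share of 20% to 50% and no excess from later exposure, a true first-trimester ratio of 2 would read as 1.20 to 1.50, and a ratio of 3 as 1.40 to 2.00. Because no comparative analysis is planned, the consequence is a descriptive table that could be misread. No test or confidence statement is invalidated. The infant search window is an unstated rule that needs stating; unequal ascertainment has not been shown.

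**What to change.** In Section 9.7.2.4:

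1. Report malformation prevalence in both cohorts by gestational age at cohort entry (before 14 weeks from the last menstrual period versus later). Show the first-trimester stratum explicitly beside the overall figure, subject to sample size. For comparators, define timing at the cohort entry encounter. The split is needed in both cohorts because neither pregnancy nor gestational age is among the pre-specified propensity score covariates in Section 9.3.3, so the gestational mix at entry may differ between them.
2. State one fixed infant claims-search window counted from birth, the same for every infant, and say whether the mother's one-year follow-up limits it. Choose its length from the actual last service date in the extract. A 90-day window, for example, would not fit the outermost due date if service dates ended on 31 March 2025.

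The cost is one table split, using timing that is already planned, and a sentence or two of text. The downside is smaller cells and wider intervals in each stratum, and the first-trimester stratum may prove too small to report.
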